Temple injections have rarely been associated with visual disturbances and blindness. Most of these have been reported with the use of fat or with HA treated in the glabellar or nasolabial fold area. Yanyuan et al.^{xiii} reported 13 cases of visual disturbance in Beijing China after facial filler injections; 4 of these were treated in the temple area with fat injections and none were treated with HA in the temple area. Park et al.^{xiv} reported 12 patients that developed retinal artery occlusion after facial filler injections; 4 of these were treated with HA, but none in the temple. (The glabella and nasolabial folds were treated). Lazzeri et al.^{xv} reviewed twenty- nine articles that described 32 patients that developed blindness after facial injections. Only 2 of these were treated with HA and neither was treated in the temple (The glabella, cheek and nasal tip were treated.) In all reports, eye pain occurred immediately after injection and was often accompanied by dizziness and nausea. Blindness has been reported to the FDA as an adverse event to HA fillers injected near the eye.^{xvi} For this reason, patients will be closely monitored post injection and visual assessments will be conducted at baseline and at the end of each injection visit using the “Vision Test” application on the iPad.

These unanticipated AEs will be reported to the FDA and IRB no later than 10 working days after the UADE onset.

If any of these UADE events occur, enrollment of this trial will be halted immediately. The patient will be sent to Bascom Palmer Eye Institute for Evaluation.

- Blindness
- Loss of visual field noted on exam by PI

Loss of Visual Acuity confirmed by iPad app or Snellen Visual Chart Mitigation of Risk

When reviewing the literature about visual disturbances caused by facial injections, it appears that the highest risk areas are injections of the glabella and nasolabial fold areas, which will not be treated in this study. Loss of visual acuity from injections in the temporal area likely occurs from retrograde embolism of ophthalmic arterial system. Multiple authors^{xvii} have discussed the ways of preventing retrograde embolism and mitigating the risk of visual disturbances and they include:

- 1) Aspiration prior to injection
- 2) Injecting slowly and with minimal pressure
- 3) Stop injection if resistance is felt
- 4) Fractionated incremental injections avoiding bolus injections
- 5) Limited total volume of substance injected

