- 6) Use of small syringes (1cc or less) to minimize injection pressure
- 7) Use of smaller needles (27.5 or smaller) to slow injection speed

These precautions will be used in this study.

Vision Assessments:

An application on the iPad called “vision test” will be used to assess visual acuity. The “visual acuity” tab will be used. If for some reason the application is unavailable, a Snellen vision test will be used with the patient standing 20 feet away from the chart and one eye covered. If the iPad app is used, the iPad or iPhone will be held at arm’s length and one eye will be covered according to the application instructions. The iPad program has a disclaimer that it does not replace an eye exam from a doctor, but this test will be used to track changes from baseline so it will be sensitive enough to suit the purpose of identifying a visual deficit induced by filler which is more likely to be manifested as a visual field defect than a change in visual acuity.

Treatment Plan for Unexpected Adverse Events

Arterial occlusion with no visual disturbance

All subjects will remain in the clinic for observation for 15 minutes after injections. The study team will be instructed to watch for the signs of arterial occlusion, which include intense skin pain, blanching of the skin, and a reticulated vascular pattern in the area of injection. This usually occurs within 15 minutes of treatment. Subjects will be instructed to call the office if they experience moderate to severe pain or skin blanching. If signs of arterial occlusion occur, the treatment plan is as follows:

- 1) Injections of hyaluronidase into the area that HA was placed prior to the symptoms
- 2) Use of anticoagulative therapy, i.e. aspirin, ibuprofen
- 3) Application of nitropaste to the treated area to encourage vasodilation for 10 minutes
- 4) Follow up as determined necessary by the investigator

Treatment Plan for Unanticipated Adverse Device Effect

Visual Disturbance:

These unanticipated AEs will be reported to the FDA and IRB no later than 10 working days after the UADE onset. If any of these UADE events occur, enrollment of this trial will be halted immediately. The patient will be sent to Bascom Palmer Eye Institute for Evaluation.

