The use of JUVÉDERM VOLUMA™ XC in the temporal areas of the face will show an improvement of ≥ 1 grade as compared to pre-treatment by a trained investigator and the subject's satisfaction with their appearance will improve by ≥ 1 grade as compared to pre-treatment scores. The investigator will assess the treated patients using the Temporal Fossa Rating scale (see Appendix A). The risk of mild adverse side effects is expected to be less than 5 percent, with no expected incidences of moderate to severe adverse events.

DESIGN

This study will be an open label, single center study, composed of a treating investigator and 30 subjects.

30 subjects will be injected with JUVÉDERM VOLUMA™ XC to their right and left facial temporal regions at the baseline visit. Subjects will receive up to 4, 1mL syringes of JUVÉDERM VOLUMA™ XC for their initial injection and a maximum of 6, 1mL syringes of JUVÉDERM VOLUMA™ XC for the study. Subjects will undergo one touch-up injection approximately 2 weeks post initial treatment, and will continue to be evaluated at month 1, month 3, and month 6. All treated subjects with the study product may exit the trial at month 6.

The baseline visit will consist of completion of the informed consent, medical history, concomitant medications and procedures, pregnancy screen via urine pregnancy test (females of child bearing potential only), and evaluation of both inclusion and exclusion criteria. Upon determination of qualification for study participation, subject's assessments (see Appendices C and E), investigator assessments, and photography will be completed. Subjects will proceed to

the initial injection, if no wash out is required. The treating investigator will inject a maximum of 4, 1mL syringes of JUVÉDERM VOLUMA™ XC into the subject's facial temporal area (see Figure 1). Treating investigator may use ice packs to diminish swelling prior to; or post injection. After the initial treatment, subjects will receive a treatment diary (see Appendix F) spanning from initial treatment to touch up treatment in order to monitor treatment site, patient reaction to study product and comments. The diary will be completed daily post-injection for 14 days post each injection. Treated subjects will undergo photos post-treatment as well. Subjects will receive a phone call three days post-treatment for a follow up.

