Subjects will return two weeks post initial injection for a possible touch up. The treating investigator will determine whether a touch up treatment is necessary. Prior to treatment, subject diaries will be collected and reviewed. All AEs/SAEs, changes in concomitant medications and concomitant procedures will be documented. Per the treating investigator's discretion, the subject may or may not qualify for a touch up. The subject will undergo photos. If treatment is necessary, subject will undergo same procedures as the initial injection visit. Post-treatment photos will be taken and subject will receive another diary and 3 day post injection phone call.

Follow up visits will consist of documentation of AEs/SAEs, changes in concomitant medications and changes in concomitant procedures at the beginning of the visit. The investigator and subject will complete their respective assessments and photos will be taken.

ENDPOINTS

The primary endpoint of this study is to determine the efficacy and safety of JUVÉDERM VOLUMA™ XC when used in the facial temporal regions based on the change in the score of the investigator's Temporal Fossa Scale. The secondary endpoints are the 2-point change in the scale of Subject's Satisfaction of Facial Appearance and Investigator's Satisfaction Scale.

STUDY PROCEDURES

PROCESS OF CONSENT/SUBJECT COMPREHENSION

All subjects will first be given the informed consent to read over by themselves. One of the investigators and a qualified member of the research staff will then review the informed consent with the prospective subject. The subject will then be allowed ample time to ask any questions about the study, and all questions will be answered. The person obtaining consent will ensure that the subject has a clear understanding of the study procedures. Once all questions are answered and the subject chooses to enroll in the study, the subject will be asked to sign the IRB-approved informed consent document. No study procedures will be conducted prior to signing the informed consent. Each subject will receive a copy of their signed informed consent for their information.

CONSENT FORMS

IRB approval will be obtained prior to use of the consent form.

INCLUSION CRITERIA

Subjects must meet the following inclusion criteria to be enrolled in this study:

Be willing and able to read and sign the informed consent and other study documents.

Male or female, 35- 75 years old.

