Have a history of migraines or frequent headaches, as determined by the PI.
Have blindness or partial vision loss in either eye.
Have received any other therapy, which, in the opinion of the investigator, could interfere with safety or efficacy evaluations.
Current enrollment in an investigational drug or device study or participation in such a study within 30 days of entry into this study.
Patient who has a condition or is in a situation that, in the investigator's opinion, may put the patient at significant risk, or may significantly interfere with the patient's participation in the study.
Have received anti-coagulation, anti-platelet, or thrombolytic medications (e.g., warfarin), anti-inflammatory drugs (NSAIDs, e.g., aspirin, ibuprofen), or other substances known to increase coagulation time from 10 days pre- to 3 days post injection. A wash out period of 10 days is allowed.
Have undergone immunosuppressive therapy, chemotherapy, biologics or systemic corticosteroids within 3 months prior to each study visit.

DRUG DISPENSING

A total of 30 subjects will be treated with JUVÉDERM VOLUMA™ XC.

The JUVÉDERM VOLUMA™ XC study products will be placed in a locked temperature monitored study cabinet for the duration of the trial. On treatment day, Baseline/Visit 1, subjects will receive a treatment of a maximum of 4 total, 1 mL syringes of JUVÉDERM VOLUMA™ XC. Maximum drug allotted per subject including initial treatment and touch up treatment will be 6, 1 mL syringes.

SCREENING/ VISIT 0

Before enrollment into the study, subjects must sign the informed consent form and the HIPAA form. Once the subject has signed the informed consent and HIPAA, the following procedures will be conducted:

- Inclusion and exclusion criteria will be reviewed.
- Demographic information will be recorded.
- Medical/surgical history and concomitant medications will be obtained from the subject and recorded.
- Physical exam will be performed including vital signs and visual assessments
- The investigator will rate the subject's facial temporal areas using a scale with photo guide as follows (1 = Convexity, 2 = Flat, 3 = Mild Concavity, 4 = Moderate Concavity, and 5 =Severe Concavity). This scale will be referred to as the Frontal Temporal Fossa Rating Scale.
- Inclusion and exclusion criteria will be reconfirmed
- Subjects who do not meet the inclusion and exclusion criteria will be marked as screen failures

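### The automatic halt after a vision event stops enrolment only, leaving touch-up injections in subjects already treated to the treating investigator's discretion

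*Combined protocol and SAP*

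**What the plan says.** The rule appears twice in the same words, under UNANTICIPATED ADVERSE DEVICE EFFECT (UADE) and under Treatment Plan for Unanticipated Adverse Device Effect: "If any of these UADE events occur, enrollment of this trial will be halted immediately". The first of these sections lists three triggers: blindness, visual field loss found by the PI, and "Loss of Visual Acuity confirmed by iPad app or Snellen Visual Chart". The affected patient is referred for eye evaluation. On reporting, the text is: "These unanticipated AEs will be reported to the FDA and IRB no later than 10 working days after the UADE onset". Neither section says what happens to injections in other subjects, or when the halt may be lifted.

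On the second injection, DESIGN first says "Subjects will undergo one touch-up injection approximately 2 weeks post initial treatment". Later in the same section it makes this the treating investigator's decision: "the subject may or may not qualify for a touch up". The Visit 2 section sets the visit at week 2 ± 3 days and again makes the touch-up depend on that investigator finding it indicated. DESIGN and DRUG DISPENSING cap the product at 4 mL for the first treatment and 6 mL in total.

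Two other provisions could stop treatment. PROTECTION AGAINST RISKS allows an investigator to stop participation for subjects' health or safety. SUBJECT DISCONTINUATION allows the investigator to withdraw an individual. Both permit a stop; neither requires one.

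**The concern.** The protocol ties the hazard to the injection. It attributes vision loss after temple treatment to retrograde embolism and lists limited injected volume among its precautions. A touch-up follows the same procedures as the first treatment. A rule that blocks a new subject's first injection but not a treated subject's second leaves the same kind of exposure open.

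The Vision Test and visual field exam at Visit 2 compare each subject with that subject's own baseline. They do not respond to an event in someone else. What is at stake is further injection in other subjects after an outcome that the sponsor judged grave enough for an automatic stop, before that outcome has been evaluated.

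**Working it through.** The plan gives no stopping boundary or error rate to reproduce. The check compares the scope of the rule with the stated visit windows.

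**Inputs.** Touch-up visit: 14 ± 3 days after first injection (Visit 2 section). Product caps: 4 mL at first treatment, 6 mL in total (DESIGN, DRUG DISPENSING). Report limit: 10 working days from onset (UADE section). Sample size: 30 (DESIGN). Accrual rate: not stated.

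**Touch-up window.** 14 − 3 = day 11 to 14 + 3 = day 17 after first injection.

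**Product still allowed.** At least 6 − 4 = 2 mL per subject. This is a remaining cap for both temples together, not a planned dose.

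**Position relative to an event in another subject.** Put the event on day 0 and let a subject's first injection be d days earlier. The touch-up window is then day 11 − d to day 17 − d.

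| d | Window | Position |
|---|---|---|
| 0 | +11 to +17 | wholly after the event day |
| 3 | +8 to +14 | wholly after the event day |
| 10 | +1 to +7 | wholly after the event day |
| 11 | 0 to +6 | opens on the event day |
| 17 | −6 to 0 | closes on the event day |

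The whole window lies after the event day when 11 − d ≥ 1, that is d = 0 to 10. For d = 11 to 17 the window opens on or before the event day, so the touch-up may already have been given. Those subjects count only if it has not.

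**Against the report limit.** Ten working days is 14 calendar days for a weekday onset with no holidays (13 for a Saturday, 12 for a Sunday). For every d from 0 to 10 the window opens by day 11, before the limit on any of these counts. With a weekday onset it also closes by the limit when 17 − d ≤ 14, that is d ≥ 3. So for d = 3 to 10 the whole window can pass after the event and by the last permitted reporting day. With a Sunday onset this holds for d = 5 to 10.

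**End of accrual.** Once subject 30 is enrolled, an enrolment halt has no effect, while touch-ups can continue for up to 17 days after the last first injection.

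**Number of subjects.** Without an accrual rate, all that can be said is the logical bound of 0 to 29 other subjects (30 − 1).

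**The case against.** The practical gap is small. This is a "single center study, composed of a treating investigator and 30 subjects". That investigator would almost certainly know of the event, and no touch-up happens unless that person decides it is indicated. The power to stop participation for safety is not confined to one individual. The protocol also describes such events as rare, and none of the three case series it cites includes a visual event after hyaluronic acid in the temple. All of this stands, and it keeps the point modest. It does not remove the gap: the same investigator could equally have stopped enrolment by judgement, yet the sponsor chose a mandatory rule there.

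A reader might infer more than the documents support:

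- *That the protocol directs touch-ups to go on after a vision event.* It does not. It is silent, and discretion remains.
- *That everyone injected in the preceding 17 days faces a further injection.* Those injected 11 to 17 days before may already have had it.
- *That touch-ups would come before the report to the FDA and IRB.* The 10 working days is an upper limit, so the overlap shows only that this is possible.
- *That first injections pending after washout also escape the halt.* This depends on a literal reading of who is enrolled in SCREENING/ VISIT 0. DESIGN places the determination of qualification at the baseline visit, and Visit 1 is described as for subjects who meet the entry criteria. Eligibility is reviewed again if baseline falls on a later day, and the exclusion criteria cover anyone whose condition or situation "may put the patient at significant risk" in the investigator's opinion.

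**Conclusion.** The point holds as a cheap improvement to a stated safety rule. Followed exactly, the rule stops new entries and leaves second injections to one person's judgement. After the last enrolment it stops nothing.

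In size, the subjects clearly within the gap are those first injected 0 to 10 days before the event, each with at least 2 mL still allowed. Those injected 11 to 17 days before are added only if still untouched. The count of subjects cannot be given. The day ranges rest only on the stated windows; the comparison with the reporting limit also assumes no public holidays. Nothing here shows that a touch-up would in fact be given after such an event.

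**What to change.** In both sections that state the halt, write: *If any of these events occurs, enrollment and all further study injections, including touch-ups, stop at once until the affected patient's eye evaluation is complete and the event has been reported to the FDA and IRB.* Add that a touch-up that cannot be given within the week 2 ± 3 day window is omitted. This avoids late touch-ups running into the Month 1 rating. Referring to all study injections also makes the washout question moot.

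The cost is one sentence in two places, the short addition on late touch-ups, and some missed or delayed elective touch-ups. Some of these could follow a false-positive app result: the acuity trigger has no stated threshold, and Vision Assessments concedes: "The iPad program has a disclaimer that it does not replace an eye exam from a doctor". The same result already halts enrolment under the present text. Requiring IRB agreement before resumption would go beyond the gap. No turnaround is stated, and the touch-up window is only seven days long.

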Hyaluronidase will be injected into the temple area in the area of Voluma injection or ischemia. 0.5- 1.0 cc will be used per ischemic site. Only the affected areas will be treated. After injection of hyaluronidase, the injected area will be massaged. If the filler has migrated to a distant location, the hyaluronidase will be injected in the area where the vessel appears to be ischemic and the surrounding vascular area will be massaged for 2 minutes to encourage penetration of the hyaluronidase into the vessel. A warm compress may be used to increase blood flow to the area. Nitropaste should only be used in patients with no history of heart disease. After application of nitropaste, if the patient feels dizzy, vital signs should be taken and the patient should be given juice. If blood pressure drops below 90/60, the nitropaste should be removed immediately and the patient's blood pressure should be closely monitored. If it does not rise in 5 minutes and the patient continues to feel dizzy or unwell, 911 will be called. If visual disturbances persist- the patient will be transferred to the Bascom Palmer ER. If the ischemia persists, the Pi will decide if the patient needs to go to the ER or if the ischemia is mild (and not affecting vision) the patient will be placed on one aspirin every 4 hours, and warm compresses and seen within 18 hours by the PI to check for revascularization. NOTE: THE PATIENT WILL NOT BE PLACED ON ASPIRIN IF A VISUAL DISTURBANCE OCCURS IN CASE SURGICAL INTERVENTION IS NECESSARY.

Summary of background

Hyaluronic acid injections have been used safely in the temples in many patients by many physicians, including [name]. Risks, however, do exist but do not seem to be as common as in patients treated with HA fillers in the nasolabial folds. Clinical studies using JUVÉDERM VOLUMA™ XC have demonstrated efficacy, safety and duration of the dermal filler in the mid-facial area. Many doctors are advocating the use of VOLUMA™ in the temples, therefore, there is a need to conduct clinical studies of augmentation in the temporal regions of the face in order to develop an approach that mitigates risk and management of adverse events. The purpose of this study is to evaluate efficacy and safety using a cautious injection technique with a clear plan for recording and treating adverse events.

STUDY DESIGN

CLINICAL HYPOTHESIS

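### The list for arterial occlusion without visual disturbance gives aspirin or ibuprofen without first testing vision, and omits the heart-disease limit on nitropaste

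*Combined protocol and SAP*

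**What the plan says.** All places below are in the combined protocol and SAP.

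**The list.** In the Treatment Plan for Unexpected Adverse Events, the part on arterial occlusion with no visual disturbance tells staff to watch for intense skin pain, blanching and a reticulated pattern. Of the onset it says: "This usually occurs within 15 minutes of treatment". If such signs appear, it lists hyaluronidase, then "Use of anticoagulative therapy, i.e. aspirin, ibuprofen", then "Application of nitropaste to the treated area to encourage vasodilation for 10 minutes", then follow-up as the investigator sees fit. No condition is attached to the second or third item.

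**The limits.** Both stand later, in the section Use of hyaluronidase. On nitropaste: "Nitropaste should only be used in patients with no history of heart disease". On aspirin, in capitals: "THE PATIENT WILL NOT BE PLACED ON ASPIRIN IF A VISUAL DISTURBANCE OCCURS IN CASE SURGICAL INTERVENTION IS NECESSARY". For persisting ischemia, the same section allows aspirin on a condition: "if the ischemia is mild (and not affecting vision) the patient will be placed on one aspirin every 4 hours".

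**The vision checks.** The section on unanticipated adverse device effects says that "visual assessments will be conducted at baseline and at the end of each injection visit". The Visit 1 procedures have the treating investigator review the result before the subject is dismissed. Under Vision Assessments, a filler-induced deficit is described as one "which is more likely to be manifested as a visual field defect than a change in visual acuity".

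**The visual plan.** The Visual Disturbance plan notes that the reported visual cases all had immediate eye pain, many with dizziness and nausea. It gives the treatments to use when these symptoms are noted.

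**The concern.** The reason given for barring aspirin when vision is disturbed is that surgery may be needed. That bar protects the subject only if someone has established that vision is intact before aspirin is given. The list starts on signs in the skin, and its heading presumes the answer about the eye without saying how to obtain it. By the protocol's own account, the deficit to expect is a field defect, which a subject may not notice or volunteer.

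At stake is an antiplatelet dose given to a subject whose visual deficit has not yet been looked for. A smaller matter is nitropaste reaching a subject with a cardiac history because the list does not point to the limit. Neither bears on sample size, endpoints or analysis.

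**Working it through.** The plan has no figure to reproduce. The check is a comparison of the places that govern the same emergency.

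1. **What starts the list.** Skin signs only. No item asks about the eye or tests it.
2. **What aspirin requires.** Use of hyaluronidase makes it conditional on vision: barred if vision is disturbed, and allowed for persisting mild ischemia only if vision is unaffected. The list carries no such condition.
3. **When vision is formally checked.** At the end of the injection visit, with review before dismissal at both injection visits. Neither time is tied to starting aspirin or ibuprofen. At Visit 2 the two tests are listed ahead of the touch-up and only the review is listed after it, although list order does not fix timing.
4. **When occlusion appears.** Usually within 15 minutes of treatment, so possibly before an end-of-visit check. Subjects who telephone later with pain or blanching have no stated vision check before the list is applied.
5. **Taken together.** Following the list as written, aspirin may precede any test of acuity or field. The documents do not say that it must.
6. **Nitropaste.** The list is unconditional, while Use of hyaluronidase limits nitropaste to subjects without past heart disease. A cardiac history is not a named exclusion: uncontrolled systemic disease is excluded, as is any condition that the investigator thinks puts the subject at significant risk. Controlled heart disease can therefore pass. Medical history is recorded at screening, so the information exists, but the list does not send staff to it.

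**Size.** The background puts arterial occlusion below 2% of patients treated with hyaluronic acid filler, mostly in the nasolabial and glabellar areas, and the principal investigator has seen none in the temple. With 30 subjects, a loose ceiling is 30 × 0.02 = 0.6 occlusions. At an assumed 0.1% it is 30 × 0.001 = 0.03. These are counts of occlusions, not of aspirin given with a missed deficit. The second count also needs the share of occlusions with an unrecognised deficit, which the documents do not give, so it is not computed here.

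**The case against.** The strongest reply is that the protocol already covers this. Both limits are written in the same body of management text, the aspirin note in capitals, and a general limit need not be repeated in every list. The list's heading confines it to cases without visual disturbance, and a separate visual plan follows with its own symptom trigger. Since all reported visual cases had immediate eye pain, most would be recognised. The post-injection Vision Test at Visit 1 is not fixed to after the 15 minutes of observation, the four items are not said to be strictly sequential, and nothing stops the investigator from testing vision at once. A licensed physician experienced in these injections gives all treatments, and the principal investigator has managed vascular occlusions before.

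Most of this stands. It rules out three readings that a reader might infer:

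- That the safeguards are missing or that the sections contradict each other. They do not: Use of hyaluronidase states both limits.
- That aspirin would always or usually come before the vision test. The text leaves that open.
- That subjects with heart disease would be given nitropaste. That assumes the written limit is overlooked, for which the documents give no basis.

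What remains is narrower. Symptoms lower the chance of an unrecognised deficit, but they do not replace an examination when a silent field defect is the loss to look for. No provision places that examination before aspirin or ibuprofen.

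**Conclusion.** The point holds as a minor one. The vision part is a real gap in sequence: a list started by skin signs gives aspirin or ibuprofen without first testing vision, while the formal check comes only at the end of the visit or before dismissal. That runs against the intent of the capitalised note. The nitropaste part is a consistency edit, since the limit already governs.

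Confidence is high on what the list contains and on where the checks are placed. How often a subject would be affected is rare and cannot be quantified from the documents. The conclusion rests on the text, not on a rate.

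A reader might also see a conflict between the aspirin in the list and the four-hourly aspirin for persisting mild ischemia. The text does not say whether the second continues the first or is a separate indication. That is a question for the investigator to clarify and is not part of this finding.

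**What to change.** Amend the list for occlusion without visual disturbance as follows.

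- Keep hyaluronidase as the immediate first step.
- Before the second step, ask about eye symptoms and do the acuity test and confrontation field exam already used in the study.
- If acuity is worse than at baseline, or any field deficit is found, withhold aspirin and move to the Visual Disturbance plan. Count a field deficit whether or not a baseline field was recorded: Visit 1 lists the field exam after injection, and the visual assessments at screening are not specified.
- Withhold ibuprofen as well if the investigator confirms. The capitalised note names only aspirin, but the list groups the two.
- Add to the nitropaste step that it applies only to subjects without past heart disease, with a reference to Use of hyaluronidase. State that permitted nitropaste does not wait for the vision check.

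The cost is a few lines of wording and a brief delay to aspirin or ibuprofen. Hyaluronidase and permitted nitropaste are not delayed, and a subject with no deficit on these checks still receives aspirin or ibuprofen.
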